The average U.S. consumption of dietary fiber is only 20-50% of recommended intake levels. Resistant starch (RS) is a naturally occurring type of fiber that is resistant to human digestion, but may be fermented by the human gut microbiota and affect systemic markers of health. RS is associated with decreased insulin resistance, systemic markers of inflammation, and serum endotoxin levels in both animal models and humans. Our aim is to see if a 2 months regime of eating common foods made with RS will change markers of inflammation and insulin resistance as well as the composition of gut bacteria in colorectal cancer survivors.

Study Overview

Patients with a history of stage I-III colorectal cancer who have completed colorectal cancer treatment will be recruited from the SCCA GI Oncology Clinic. Patients will participate in an 8-week randomized, controlled trial testing foods made with resistant starch vs foods made with corn starch. All food products will be made under strictly controlled conditions in the Fred Hutch Human Nutrition Lab and will include a variety of common foods such as scones, muffins, pudding and cookies. The only difference between the products is that some products will be made with resistant starch and some will be made with corn starch. Both investigators and participants will be blinded to their randomization assignment.

Randomized, Controlled Trial of Resistant Starch in Stage I-III Colorectal Cancer Survivors Pilot Study: The Fiber for Health After Cancer Study

Eligibility criteria include: 1) history of diagnosed AJCC stage I-III colorectal adenocarcinoma; 2) completion of all treatment of colorectal adenocarcinoma within the past 4-36 months; 3) ECOG Performance Status of 0, 1, or 2 (per physician); 4) age ≥ 18 years at diagnosis; 5) absence of any active inflammatory bowel disorder; 6) no use of antibiotics within 3 months prior to enrollment; and 7) ability to consent and follow study protocol.

Stool sample will be collected three times in the privacy of each person's home using a kit and instructions provided. Fasting blood samples will be collected at baseline and week 8 at the Fred Hutch Prevention Center.

After agreeing to participate and signing informed consent, participants will be randomized to receive the active intervention (daily foods containing resistant starch) or control intervention (daily foods containing corn starch).

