The intervention will use commercially available RS-2 (Hi-Maize) that will be prepared into common bakery items, such as muffins, scones, as well as beverages such as smoothies. Control products will use the same recipe but will be prepared with regular corn starch. The RS will be Hi-Maize, a corn starch made solely from hi-amylose maize. This product is commercially available from, among others, King Arthur Flour, Honeyville and Amazon. It has been used in many published studies⁸⁵⁻⁹³ as well as at least 20 studies currently listed in ClinicalTrials.gov. Dose range has been from 15g/day to 47g/day and study duration from 1 to 8 weeks. Some people may experience flatulence and perhaps some bloating due to the higher fiber content added to their diet, therefore we will have participants do a stepwise escalation that will allow for better adaptation to the target dose of 30g. RS per day. In the first two weeks participants will consume one study food with 15 g RS per day and starting in the third week participants will consume two study foods for a total of 30g RS per day for 6 weeks. Participants will be provided with a variety of options to allow for variety. No other dietary changes will be required. Participants may consume their usual diet and participate in their usual activity throughout the study. All products will be produced at the Human Nutrition Lab in the Fred Hutch Prevention Center. See Figure 2.

Systemic inflammation will be measured as serum C-reactive protein (CRP)/albumin ratio and adiponectin. Insulin resistance will be assessed using the homeostasis model of assessment-insulin resistance (HOMA-IR). Gut microbial community structure (16S rRNA sequencing), and gut metabolites will be compared between intervention and control groups for generation of hypotheses for protective prebiotic effects on gut microbial taxa.

In order to determine whether an RS dietary intervention can potentially affect gastrointestinal tumorigenesis in high-risk individuals, participant fecal microbiota sampled will be transplanted into colorectal tumor-prone mice ([name], UW IACUC protocol # 4418_01).

[figure not shown]
Primary Aim: To determine the feasibility of an 8-week dietary intervention testing foods made with resistant starch compared to foods made with corn starch in patients who have completed treatment for stage I-III colorectal cancer. Feasibility will be assessed based on trial accrual, intervention adherence, and trial retention.

Secondary Aims:

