2. ELIGIBILITY CRITERIA

Inclusion:

1. History of diagnosed AJCC stage I-III colorectal adenocarcinoma
2. Completed all treatment of colorectal adenocarcinoma within past 4-36 months.
3. Current ECOG Performance Status of 0, 1, or 2 (per physician)
4. Age ≥ 18 years at diagnosis
5. Ability to consent and follow study protocol

Exclusion:

1. Active cancer
2. Prior diagnosis of diabetes that is currently uncontrolled (defined as Hgb A1c >8.0)
3. Active inflammatory bowel disease (i.e., patients who are symptomatic despite medical therapy). This includes Irritable Bowel Syndrome, Crohn's Disease, or any other inflammatory bowel disorder
4. Known food allergy/intolerances to wheat, gluten, dairy or eggs
5. Use of antibiotic(s) within the last 3 months prior to enrollment
6. Women who are pregnant and/or breastfeeding
7. Current BMI $< 18.5 \text{ kg/m}^2$
8. Uncontrolled constipation
9. Inability to speak and fully understand English

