3. RECRUITMENT, APPROACH, AND CONSENT

Study investigators and staff will identify potentially eligible participants via the SCCA electronic health record. Eligibility and exclusion criteria will be checked and confirmed in the electronic health record. The SCCA physician caring for the identified patient will then be contacted to confirm appropriateness and grant permission for the patient to be approached for study participation.

In addition, potentially eligible participants will be ascertained by SCCA Survivorship Clinic staff who will screen survivor clinic records and notify study staff of potentially eligible participants. Survivorship clinic staff will provide eligible medical record numbers only for patients for whom the SCCA survivorship clinic care provider provides permission for the patient to be approached. Eligibility and exclusion criteria will be confirmed by study staff in the SCCA electronic medical record, upon which the approach process will be initiated as described below. In addition, the study brochure will be posted at the SCCA Survivorship Clinic. Persons interested in the study can contact the research study coordinator at the contact phone and/or email address provided in the brochure. The study coordinator will then conduct eligibility screening utilizing the telephone screening script procedure as per Appendix 3.

Patient contact will first consist of a mailed recruitment packet from study investigators introducing the study and inviting them to participate. This will be sent to the study candidate by both email and US Mail. The recruitment packet contains (1) an approach letter introducing the study and inviting the patient to participate and (2) a study brochure. In the letter, potential participants are invited to call study staff if they are interested in learning more about the study or if they wish no further contact. (See Appendices 1 and 2 for the approach letter and study brochure).

If a patient does not contact the study staff within 3 days of mailing the recruitment packet, study staff follows up with an email and screening telephone call. Up to 2 emails and 3 call attempts to reach the participant are made within a 1-week period. If the phone is not answered after attempt

Randomized, Controlled Trial of Resistant Starch in Stage I-III Colorectal Cancer Survivors Pilot Study: The Fiber for Health After Cancer Study

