5. INTERVENTION

Active group: Resistant Starch @ 15g/day during weeks 1 and 2, and @ 30g/d for weeks 3-8 (8 weeks total on study). If participant is not able to tolerate the higher doses they may stay at the maximum tolerated dose for the remainder of the study. (See Dosage Modification Instructions in Section 6, below). The Resistant Starch will be Hi-Maize, a RS2 corn starch from hi-amylose maize. This product is commercially available from, among others, King Arthur Flour, Honeyville, Amazon. It has been used in many published studies⁸⁵⁻⁹³ as well as at least 20 studies currently listed in ClinicalTrials.gov. The dosage in our study is comparable to other studies and the product is well tolerated with the main issues being gastrointestinal discomforts such as flatulence and feeling bloated. Studies report few dropouts due to these symptoms.

Control group: will receive similar size and number of items as the active group, made with regular corn starch. If participant is not able to tolerate the higher doses they may stay at the maximum tolerated dose for the remainder of the study. (See Dosage Modification Instructions in Section 6, below).

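### Exclusion 4 screens for allergy or intolerance to wheat, gluten, dairy and eggs but omits corn, although maize starch is in the study foods of both arms

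*Combined protocol and SAP*

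**What the plan says.** Section 2, Exclusion 4 is the only food-related exclusion: "Known food allergy/intolerances to wheat, gluten, dairy or eggs". It is a closed list of four items, with no catch-all for other ingredients. The shorter eligibility list in the Section 1 overview has no food-allergy criterion at all.

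On the active foods, Section 1 says "The RS will be Hi-Maize, a corn starch made solely from hi-amylose maize", and Section 5 agrees: "The Resistant Starch will be Hi-Maize, a RS2 corn starch from hi-amylose maize". On the control foods, Section 1 says "Control products will use the same recipe but will be prepared with regular corn starch". It also states "The only difference between the products is that some products will be made with resistant starch and some will be made with corn starch".

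Two general provisions could bear on the point:

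- Inclusion 5 in Section 2 requires "Ability to consent and follow study protocol".
- For patients found through the health record, Section 3 has the treating physician "contacted to confirm appropriateness and grant permission for the patient to be approached for study participation". Patients found through the Survivorship Clinic likewise need their provider's permission.

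Section 3 also opens a third route: "Persons interested in the study can contact the research study coordinator at the contact phone and/or email address provided in the brochure". For these people it describes telephone screening by the coordinator and states no physician check.

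**The concern.** The plan screens by named ingredient, and the four names fit the bakery and dairy base of the foods. The omitted ingredient is the one that defines the comparison and that the plan places in every study food. A screener who works through the exclusions for someone with a known corn allergy or intolerance finds none that applies. Randomization gives no protection, because both arms receive maize starch, and a participant cannot avoid it by choosing among the products.

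What is at stake is first the safety of such a participant. A lesser matter is that an avoidable reaction could, in some circumstances, cost a participant on adherence or retention, two of the three feasibility criteria in Section 8.

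**Working it through.** No figure in the plan depends on this point, so the check is mainly a comparison of texts.

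**1. Ingredients against exclusions**

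| Item | In the study foods, per the plan | Named in Exclusion 4 |
|---|---|---|
| Maize starch | Yes, both arms (Sections 1 and 5) | No |
| Wheat, gluten, dairy, eggs | No ingredient list is given; plausible for the scones, muffins, puddings and smoothies described | Yes |

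**2. Other places where corn might be screened**

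- Section 2, Inclusion 5: general; names neither corn nor allergy.
- Section 3, physician or clinic permission: general; stated for the two clinic-based routes only.
- Section 6, intolerance rule: applies only after study food has been eaten, and only to related events of grade 3 or above.
- Section 7, intervention risks: gastrointestinal effects only; allergic reaction is not mentioned.
- Appendix 3 (screening script), Appendix 4 (consent form), Appendices 13 and 14 (food instructions): listed, but their text was not available.

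No available text makes corn allergy or intolerance an exclusion, a screening item or a listed risk.

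**3. Planned exposure (Sections 1 and 5)**

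- Study foods, either arm: 14 days x 1 + 42 days x 2 = 14 + 84 = 98 items.
- Resistant starch, active arm: 14 x 15 g + 42 x 30 g = 210 + 1,260 = 1,470 g.

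Control foods are to be similar in size and number. These sums show that exposure is built into both arms. They say nothing about how many people would be affected.

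**4. When retention could be affected (Sections 6 and 8)**

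Retention needs both blood and stool at 8 weeks.

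- Related event of grade 3 or above in weeks 1-2: the intervention stops, the week-2 stool and the end-of-study blood are collected, and the rest is dropped. There is no end-of-study stool, so the definition is not met.
- First such event in weeks 3-8: the dose is reduced and all collection continues. Retention need not be affected.
- A new or continuing event after that reduction: the intervention stops, but end-of-study stool and blood are still collected, within a week. Section 8 does not say whether samples taken early count as 8-week samples.
- Milder related symptoms: no change under Section 6.

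**5. Size of one loss**

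The available text gives no sample size. The 80% target is set on all enrolled participants together. If 20 to 40 were enrolled in total (an assumption), one loss would be 1/40 = 2.5 to 1/20 = 5 percentage points of pooled retention.

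**The case against.** The case on the other side is that the route to harm is narrow. The protocol consists of eating foods made with corn starch every day for eight weeks, so a person who knows of a corn allergy arguably fails Inclusion 5. Before randomization there is an approach letter and brochure or a self-referral, a scripted screening call, a mailed consent form and a consent discussion; most candidates also need a physician's or clinic's permission. The unseen screening script may ask about corn. Any list of named allergens can be called incomplete, and no analysis changes.

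Much of this stands as a limit on size. It would be too strong to say that such a person meets every inclusion criterion, because Inclusion 5 can be read against them. But that reading is left to the screener's judgement, and the plan did not rely on it for the other four ingredients. A corn question in Appendix 3 would be welcome, but the governing criteria would still not contain it.

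Three stronger readings are tempting and should not be drawn:

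- **Neither arm is safe for such a person.** The documents do not say how someone with corn allergy or intolerance responds to these starches. They support only that neither arm avoids the exposure.
- **Any reaction would count against adherence and retention.** Section 6 shows that this depends on grade, attribution and timing.
- **One loss costs 5 to 10 points of retention.** That would follow from setting one participant against an assumed arm of 10 to 20, but the target is pooled, so the figure on the same assumption is half of that.

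**Conclusion.** The gap in the written criteria is real. Exclusion 4 does not cover the ingredient the plan puts in every study food, and no other available provision names it. The two partial safeguards are discretionary, and no physician check is stated for brochure self-referrals.

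The point is mainly one of participant safety, and its practical size is probably small. The documents give no prevalence of corn allergy or intolerance, so no expected count can be calculated. An effect on the feasibility criteria is possible only in some cases, the clearest being a related event of grade 3 or above in weeks 1-2. The 2.5 to 5 points for one loss rests entirely on the assumed total of 20 to 40.

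The conclusion about the written criteria does not depend on that assumption or on prevalence. It is limited by the unseen appendices: they may reduce the practical risk, but they would not change Section 2 as written.

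**What to change.** Reconcile Exclusion 4 with the stated ingredients of the study foods. Either add corn (maize) to the listed allergies and intolerances, or state in the protocol why it is not listed. Then check that the Appendix 3 telephone screening script matches, since for brochure self-referrals that call is the only eligibility screen the text describes.

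The cost is a one-line amendment and, if needed, one question in the script. No dose, endpoint or analysis changes. The downside is the rare loss of a candidate with a known corn allergy or intolerance.

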3. RECRUITMENT, APPROACH, AND CONSENT

Study investigators and staff will identify potentially eligible participants via the SCCA electronic health record. Eligibility and exclusion criteria will be checked and confirmed in the electronic health record. The SCCA physician caring for the identified patient will then be contacted to confirm appropriateness and grant permission for the patient to be approached for study participation.

In addition, potentially eligible participants will be ascertained by SCCA Survivorship Clinic staff who will screen survivor clinic records and notify study staff of potentially eligible participants. Survivorship clinic staff will provide eligible medical record numbers only for patients for whom the SCCA survivorship clinic care provider provides permission for the patient to be approached. Eligibility and exclusion criteria will be confirmed by study staff in the SCCA electronic medical record, upon which the approach process will be initiated as described below. In addition, the study brochure will be posted at the SCCA Survivorship Clinic. Persons interested in the study can contact the research study coordinator at the contact phone and/or email address provided in the brochure. The study coordinator will then conduct eligibility screening utilizing the telephone screening script procedure as per Appendix 3.

Patient contact will first consist of a mailed recruitment packet from study investigators introducing the study and inviting them to participate. This will be sent to the study candidate by both email and US Mail. The recruitment packet contains (1) an approach letter introducing the study and inviting the patient to participate and (2) a study brochure. In the letter, potential participants are invited to call study staff if they are interested in learning more about the study or if they wish no further contact. (See Appendices 1 and 2 for the approach letter and study brochure).

If a patient does not contact the study staff within 3 days of mailing the recruitment packet, study staff follows up with an email and screening telephone call. Up to 2 emails and 3 call attempts to reach the participant are made within a 1-week period. If the phone is not answered after attempt

Randomized, Controlled Trial of Resistant Starch in Stage I-III Colorectal Cancer Survivors Pilot Study: The Fiber for Health After Cancer Study

1, a voice mail will be left, and a 2nd attempt will be made the next day. If the phone is not answered after attempt 2, a voice mail will **not** be left. If after 3 attempts to reach the participant contact does not succeed, no further attempts are made and the participant is released from study consideration.

The email and screening call is conducted as scripted (see Appendix 3). During the screening phone call, study staff assesses interest and reassesses and confirms eligibility. Eligible participants will be scheduled for a Consent Visit to be conducted either in person at the Fred Hutch Prevention Center, or virtually via telephone should telephonic consent be optimal to manage the visit in the context of the coronavirus/COVID-19 outbreak. The primary purpose of the Consent Visit is to sign informed consent. Height and weight baseline data, necessary for performing the block randomization, will be collected at the in-person Consent Visit or by participant self-report if the Consent Visit is conducted telephonically. In either case, the consent form is mailed to participants before the Consent Visit, along with driving/transportation directions and appointment confirmation information (see Appendices 4, 5, and 6).

Consent is obtained in person in the Prevention Center or by telephone by study staff at the participant's Consent Visit. If conducted telephonically, study staff conduct the Consent Visit using a *Telephonic Informed Consent Script* (Appendix 17). For telephonic Consent Visits, if after complete the informed consent discussion the participant verbally agrees to join the study, the participant is instructed to sign and date the consent form using the date of the consent call and to return the signed consent when s/he comes in for the next Study Visit. Study procedures proceed only after written informed consent is obtained.

4. DATA COLLECTION

4.a. CONSENT VISIT

As described in Section 3 above, potential participants schedule a Consent Visit with study staff to take place either in person at the Prevention Center (Arnold Building, Fred Hutch), or telephonically. After reviewing study procedures and being able to ask questions, interested participants will provide written informed consent and height and weight will be collected. After consenting, participants are randomized into the trial using a permuted block design, based on sex and 2 BMI categories (below and equal/above $BMI = 25 \text{ kg/m}^2$). Participants, investigators and study staff will be blinded to randomization condition.

At consent participants are provided with a stool collection kit and written and verbal instructions on their use as well as a blank 1) Food Frequency Questionnaire and 2) a baseline Study Questionnaire to fill out before and bring completed with them to their first intervention visit. Study staff schedule the Intervention Visit 1.

After consent, the following data will be abstracted by study staff from the SCCA/UW Medical Records.

- A. Patient and tumor characteristics at time of **initial (pre-treatment)** presentation at SCCA:
 1. Demographics
 2. Height and Weight
 3. Comorbidities
 4. Resection Surgery Date
 5. Tumor site
 6. T stage
 7. Tumor size
 8. N stage

Randomized, Controlled Trial of Resistant Starch in Stage I-III Colorectal Cancer Survivors Pilot Study: The Fiber for Health After Cancer Study

9. Number of positive nodes
10. Number of total nodes removed
11. Histologic type (i.e. adenocarcinoma)
12. Grade
13. Lymphatic invasion
14. Vascular invasion
15. Perineural invasion
16. Proximal/distal margins
17. Circumferential margin
18. Tumor-infiltrating lymphocytes
19. Peri-tumoral response

B. Colorectal cancer (CRC) treatment information:

1. Neoadjuvant treatment received **prior** to CRC surgery:
 - a. Chemotherapy Y/N and if Y, specific regimen and doses
 - b. Radiotherapy Y/N and if Y, specific regimen and doses
 - c. Dates administered
2. Post-surgical treatment received **after** CRC surgery
 - a. Specific treatment(s) received, dosages, dates
 - b. Associated co-morbidities

4.b INTERVENTION VISIT 1 – START OF INTERVENTION

Participants collect a stool sample at home the day before or morning of Intervention Visit 1. Participants receive a reminder phone call the day prior to their intervention visit 1 to remind them about the appointment and to bring the baseline stool sample and completed baseline questionnaires with them to the visit. This call is conducted in accordance with the Visit Appointment Reminder Call Phone Script (Appendix 7). In addition, participants come to the Prevention Center to provide a fasting blood draw.

After the blood draw, participants are provided with their first set of foods and instructions for eating and logging the study foods and any associated symptoms, on a daily basis.

Summary of Intervention Visit 1 Activities:

Participants turn in their completed baseline questionnaires

1. Food Frequency Questionnaire
2. Baseline Study Questionnaire

Baseline biological samples are collected:

1. Stool
2. Blood (fasting) – 10 cc

Study staff provides the participant with study supplies for the next two weeks: study foods with instructions for storage and reheating; the Daily Study Food Consumption and Symptoms Log with instructions; and another stool collection kit with instructions for the 2nd intervention visit.

Study staff also reminds the participant that staff will call the participant weekly for the next two weeks, to check in and provide the participant opportunity to ask questions (see Adherence Call Script, Appendix 15).

Alternatively, if necessary for example during the COVID-19 pandemic, this visit may be conducted telephonically (using script per Appendix 19). Should this visit need to occur by telephone, the

Randomized, Controlled Trial of Resistant Starch in Stage I-III Colorectal Cancer Survivors Pilot Study: The Fiber for Health After Cancer Study

baseline study fasting blood draw will not be collected. The participant will be instructed to collect the stool sample using the kit provided for the baseline collection.

The participant will be sent a pre-paid, same day courier return mailing label and box to return the frozen baseline stool sample and baseline questionnaires. Depending on accessibility of the participant to his/her neighborhood courier office, the participant can either take the shipment box to the courier office, or study staff can arrange for pick-up service by the courier from the participant's home. In the event of a 'shelter in place' mandate, the latter option will be used. In the event that the courier service is not operating, the participant will be instructed to keep the study materials at home, and the stool sample in his/her home freezer, until the courier service is again operational. The first supply of study foods will be couriered to the participant for receipt on the day of the Intervention Visit 1 telephone call.

4.c. DURING INTERVENTION

Participant activities during the intervention consist of the following which are completed by the participant at home.

- Daily consumption of study foods
- Daily completion of the Daily Study Food Consumption and Symptoms Log

Phone calls (once weekly through ramp up to 30g daily then every two weeks thereafter through end of study). Study staff contact the participants via telephone to monitor adherence, collect feedback about the study (feasibility, difficulties, etc.), and give a reminder about the participant's next Prevention Center Visit. See Adherence Call Script, Appendix 15).

4.d. INTERVENTION VISIT 2 – Week 2 - Day 14

Participants return to the Prevention Center on Day 14 for the Week-2 visit. Alternatively, this visit may be conducted telephonically (using script per Appendix 18). At this visit, the participant will bring in another stool sample, the completed Study Questionnaire (Week-2 Follow Up time point), and the Daily Study Food Consumption and Symptoms Log completed for days 1-13. If the participant is unable to come to the Prevention Center, the stool sample and questionnaires can be returned by mail.

Summary of Intervention Visit 2 Activities

Participants turn in their completed Week-2 follow-up questionnaires

1. Study Questionnaire (Week-2 Follow Up)
2. Daily Study Food Consumption and Symptoms Log (for Days 1-13)

Week-2 follow-up biological samples are collected

1. Stool

Study staff provides the participant with study supplies for the next six weeks. These supplies consist of: (1) instructions for weekly or every other week receipt of study foods from the Fred Hutch Human Nutrition Lab (foods will be mailed, couriered, or the participant may opt to pick up their foods in person); (2) the Daily Study Food Consumption and Symptoms Log with instructions to complete daily for days 14 through end of study; and (3) another stool collection kit with instructions for the 3rd intervention visit.

Study staff also reminds the participant that staff will call the participant every other week through end of study. The purpose of these calls is to check in, remind the participant to eat the study foods daily at the appropriate dosage levels, and provide the participant an opportunity to ask questions.

Randomized, Controlled Trial of Resistant Starch in Stage I-III Colorectal Cancer Survivors Pilot Study: The Fiber for Health After Cancer Study

These calls also will ascertain what specific study food products the participant would like to order from the research kitchen for his/her next batch of study foods, and how he/she would like to receive them (delivery method). (See Adherence Call Script, Appendix 15).

4.e. INTERVENTION VISIT 3 - END OF INTERVENTION – Week 8 – Day 56

Participants return to the Prevention Center on Day 56 for their Week-8 and final visit. At this visit, the participant will bring in a final stool sample, the completed Study Questionnaire (Week-8 Follow Up time point), and the Daily Study Food Consumption and Symptoms Log completed for days 14 through end of study. If participant is unable to come to the Prevention Center, the stool sample and questionnaires can be returned by mail.

Summary of Intervention Visit 3 Activities

Participants turn in their completed Week-8 follow-up questionnaires

1. Study Questionnaire (Week-8 Follow Up)
2. Daily Study Food Consumption and Symptoms Log (for Weeks 3-8)

Week-8 follow-up biological samples are collected:

3. Stool
4. Blood (fasting) -10 cc

Study staff provides the participant with End of Study Thank You Letter and \$50 Visa Gift Card.

Alternatively, if necessary for example during the COVID-19 pandemic, this visit may be conducted telephonically (using script per Appendix 20). Should this visit need to occur by telephone, the end-of-study fasting blood draw will not be collected. The participant will be instructed to collect the stool sample using the kit provided for the end-of-study collection.

The participant will be sent a pre-paid, same day courier return mailing label and box to return the frozen stool sample and end-of-study questionnaires. Depending on accessibility of the participant to his/her neighborhood courier office, the participant can either take the shipment box to the courier office, or study staff can arrange for pick-up service by the courier from the participant's home. In the event of a 'shelter in place' mandate, the latter option will be used. In the event that the courier service is not operating, the participant will be instructed to keep the study materials at home, and the stool sample in his/her home freezer, until the courier service is again operational.

The end of study thank you letter and \$50 thank you payment will be mailed to the participant upon receipt of the end of study stool sample and questionnaires.

4.f. MANAGING POTENTIAL DELAYS OR DISRUPTIONS TO THE STUDY CALENDAR

This component of the study protocol is added as a result of the Fred Hutch laboratory ramp down in response to the coronavirus pandemic.

In response to the pandemic, or any other unanticipated natural disaster, it is possible that the start of intervention may need to be delayed. For other participants who may have already started the intervention, the intervention may need to be stopped early. Here we describe how each of these scenarios will be handled.

Should the start of the intervention need to be delayed:

Randomized, Controlled Trial of Resistant Starch in Stage I-III Colorectal Cancer Survivors Pilot Study: The Fiber for Health After Cancer Study

In the event that a delay in the start of the intervention be necessary, the consented participant will be called and/or emailed (using script per Appendix 21). The reason for the need to delay the start of the intervention and the remainder of the study calendar will be explained to the participant. This call/email will involve either scheduling the new study intervention dates (if possible) or scheduling a date to check in with the participant again by phone to provide study status.

Should the intervention need to be discontinued early:

In the event that due to the pandemic or other natural disaster the investigators may need to terminate a participant's study intervention before the week 8 end of study timepoint, the participant will be called and/or emailed (using script per Appendix 22). The reason for the need to discontinue the study early will be explained to the participant. During the call/email, the participant will be instructed on how to complete his/her study activities, and the call/email will remind the participant that the end of study thank you letter and \$50 payment will be sent upon receipt of the participants final study questionnaires.

